### 6.1.3 Exclusion criteria

- Full anti-inflammatory dose of NSAIDs for more than 4 weeks for the duration of the axSpA symptoms.
- Prior exposure to any biologic therapy with a potential therapeutic impact on SpA, including anti-TNF therapy.
- Exposure to disease-modifying drugs (DMARDSS; i.e. methotrexate and sulfasalazine) in the last 3 months before the ileocolonoscopy.
- Exposure to systemic corticosteroid treatment in the last 14 days before the ileocolonoscopy.
- Infection(s) requiring treatment with intravenous antibiotics/antivirals/antifungals within 30 days prior to the baseline visit or oral antibiotics/antivirals/antifungals within 14 days prior to the baseline visit.
- Have a known hypersensitivity to human immunoglobulin proteins or other components of golimumab.
- History of central nervous system (CNS) demyelinating disease or neurologic symptoms suggestive of CNS demyelinating disease.
- History of listeriosis, histoplasmosis, chronic or active hepatitis B infection, hepatitis C infection, human immunodeficiency virus (HIV) infection, immunodeficiency syndrome, chronic recurring infections or active tuberculosis.
- Have a history of, or concurrent, chronic heart failure, including medically controlled, asymptomatic congestive heart failure.
- Evidence of dysplasia or history of malignancy (including lymphoma and leukemia) other than a successfully treated non-metastatic cutaneous squamous cell or basal cell carcinoma or localized carcinoma in situ of the cervix.
- Have received, or are expected to receive, any live virus or bacterial vaccination within 3 months prior to the first administration of study agent, during the trial, or within 6 months after the last administration of study agent.
- Positive pregnancy test at screening
- Female subjects who are breast-feeding or considering becoming pregnant during the study.
- Female subjects who do not use contraceptives.
- History of clinically significant drug or alcohol abuse in the last 12 months.
- Clinically significant abnormal screening laboratory results as evaluated by the investigator.
- Positive rheumatoid factor (RF) or anti-cyclic citrullinated peptide (anti-CCP) antibody at screening if the titers are crossing 3 times the upper limit of the normal.
- Subject with diagnosis and current symptoms of fibromyalgia.
- Any medical or psychological condition that, in the opinion of the investigator, could jeopardize or compromise the subject's ability to participate in this study.

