### 6.2.1 Screening visit

At the screening visit the informed consent form (ICF) will be signed and inclusion/exclusion criteria will be checked. Subsequently routine blood tests (complete blood count, electrolytes, liver function, kidney function, CRP and Erythrocyte Sedimentation Rate - ESR) and additional study samples for inflammatory and genetic markers will be taken (4x5mL serum and 3x4mL EDTA). These additional samples will be stocked pseudonymized in a prospective research biobank ("Biobank van menselijk lichaamsmateriaal van patiënten met reumatische en/of musculoskeletale aandoeningen en gezonde controles", EC 2019/0314, medical administrator: prof. dr. [name]). Also, HIV and hepatitis serology will be checked as part of the routine blood analyses and a Mantoux tuberculin skin test and a chest X-ray will be executed to exclude latent tuberculosis.

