Visits are scheduled on week 0, 2, 4, 16, 28, 40 and 52 ( $\pm$  2 weeks). If subjects have a clinically important improvement, defined as an ASDAS score < 1.3 or a decrease of at least 1.1 in ASDAS score resulting in a maximum of 2.1, subjects will continue with the same treatment. If subjects do not meet this disease activity state after a treatment with the first NSAID, a different NSAID will be installed at full anti-inflammatory dose during 2 weeks. Again, if subjects have a clinically important improvement (compared to the baseline situation before initiating the first NSAID therapy) after 2 weeks treatment with the second NSAID, subjects continue with this treatment. If this disease activity state is not reached at week 4, the NSAID treatment will be stopped and subjects will start treatment with golimumab (anti-TNF $\alpha$  therapy, 50mg every 4 weeks, subcutaneous injection) in monotherapy. At every trial visit routine blood tests (inflammatory markers at week 0, 2, 4 and a complete blood count, electrolytes, liver function, kidney function, inflammatory markers at screening, week 16, 28, 40 and 52) will be performed. Additional study samples for inflammatory markers (2x5mL serum) will be taken at every trial visit (except for the baseline visit at week 0, no additional serum samples) and stored in the prospective research biobank. After 4 weeks NSAID treatment, after 6 months golimumab treatment and at time of relapse stool samples (1 sample at each time point) and additional blood samples (site specific: only sampling of 3x10mL heparin blood in Ghent University Hospital) will be collected. The additional heparin blood samples are used immediately for functional analysis; the stool samples are stored pseudonymized in the prospective research biobank. After the trial has ended, all stool samples will be subject to biochemical and microbiome analyses (in one batch), performed by the laboratory attached to the department of Rheumatology of Ghent University Hospital.

Maximal study duration for a subject is 12 months.

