#### **6.2.7.2 Baseline**

[figure not shown]
- Laboratory investigation (site-specific: only in Ghent University Hospital 4x10mL heparin blood for additional research)
- Stool sample
- Ileocolonoscopy including for all sites routine biopsies for pathological examination (4 biopsies in ileum, 8 biopsies in colon) and extra biopsies for RNA sequencing (2 biopsies in ileum, 2 biopsies in colon) will be taken. Additional for functional analyses, site specific (only in Ghent University Hospital), also 6 biopsies in ileum and 6 biopsies in colon will be taken.
- Start treat-to-target approach

[figure not shown]
- AND if baseline visit is performed more than 4 weeks after the screening visit:
  - o Anamnesis
  - o Current and past medication (NSAID): dosage and duration
  - o Clinical examination:
    - weight, length, vital symptoms (blood pressure, heart frequency)
    - BASMI
    - Total tender and swollen joint count (TJC/SJC) (78)
    - Dactylitis assessment
    - MASES + plantar fascia + quadriceps and patellar tendon
  - o Questionnaires: cfr. 6.2.7.1 (excl. WPAI, health care consumption and EQ5D)

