## 6.6 Additional research

We will also examine non-invasive surrogate markers for gut inflammation and therefore we will collect blood samples at every study visit and stool samples at baseline, after 4 weeks of NSAID treatment, after 6 months of golimumab treatment and at time of relapse. These are to investigate e.g. the serum and fecal calprotectin levels and to perform in depth immunophenotyping (flow cytometry) and microbiome analysis. At the screening visit we will also collect additional blood samples for genetic analyses (relevant single nucleotide polymorphisms for overlap SpA and IBD). All analyses will be performed within a context relevant to the SpA concept.

All biological samples (blood, stool, gut biopsies and its derivatives) will be collected and stored pseudonymized during 20 years in the prospective research biobank of the department of rheumatology of the Ghent University Hospital (“Biobank van menselijk lichaamsmateriaal van patiënten met reumatische en/of musculoskeletale aandoeningen en gezonde controles”, EC 2019/0314, medical administrator: prof. dr. [name]). For the Imelda Hospital in Bonheiden (Center 03) these biological samples will first be stored on site as part of the prospective research biobank of the department of rheumatology of the Ghent University Hospital and shipped regularly (cooled transport at -80°C) in batch to the Gent University Hospital. The only exception concerns the gut biopsies from patients recruited at the Reuma Institute Hasselt (Center 02): these samples will be collected in Jessa Hospital, will be locally registered and stored (temporarily) in the Jessa Biobank (medical administrator: dr. [name] – no processing required except for immediate freezing) and will be transferred at once (cooled transport at -80°C) to the prospective research biobank of the department of Rheumatology of Ghent University Hospital after the study has ended. All analysis on additional study samples will be performed by the laboratory attached to the department of Rheumatology of the Ghent University Hospital (Medical Research Building, MRB). Some analyses will be conducted by the Flemish institute for biotechnology (VIB – Vlaams Instituut voor Biotechnologie).

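### For the exploratory gut-marker research, the only research serum before study treatment is drawn at screening and none at week 0, so it is not paired with the baseline ileocolonoscopy and stool, and no maximum interval is found.

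*Combined protocol and SAP*

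**What the plan says.** Section 6.2.1 places the first research blood at screening: "additional study samples for inflammatory and genetic markers will be taken (4x5mL serum and 3x4mL EDTA"). Section 6.2.2 then lists the trial visits: "Visits are scheduled on week 0, 2, 4, 16, 28, 40 and 52". It provides 2x5 mL of additional serum at each of them, with one exception: "except for the baseline visit at week 0, no additional serum samples".

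Section 6.2.7.2 schedules the ileocolonoscopy with biopsies and one stool sample at baseline. The research blood listed there is heparin blood at one centre: "Laboratory investigation (site-specific: only in Ghent University Hospital 4x10mL heparin blood for additional research"). In table 6.4 the baseline row is empty in both serum columns. Section 6.2.7.3 resumes research serum at the follow-up visits.

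Section 6.6 describes the purpose. To examine non-invasive surrogate markers for gut inflammation, it says, "therefore we will collect blood samples at every study visit", with stool at baseline and at three later points. It names serum and faecal calprotectin as examples and makes no exception for week 0.

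On timing, section 6.2.7.2 has a conditional block that begins "AND if baseline visit is performed more than 4 weeks after the screening visit". It repeats history, medication, examination and most questionnaires, but no research serum.

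**The concern.** A serum marker of gut inflammation is judged against histology and is naturally compared with the faecal marker. The baseline ileocolonoscopy is the only histology planned in patients with and without gut inflammation, because section 6.2.4 repeats the procedure only where the first one showed inflammation. If the matching serum was drawn at another visit, weeks earlier and perhaps under another drug exposure, part of any disagreement between serum and histology, or between serum and stool, may come from timing. A sample not taken at week 0 cannot be obtained afterwards: the next scheduled research serum is at week 2, when the patient is already on the study NSAID.

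**Working it through.** The plan states no figure to reproduce, so the check sets the schedule side by side.

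| Time point | Research serum | Stool | Histology | Source |
|---|---|---|---|---|
| Screening | 4x5 mL | none | none | 6.2.1, 6.2.7.1, 6.4 |
| Week 0 | none | 1 sample | all patients | 6.2.2, 6.2.7.2, 6.4 |
| Week 2, on NSAID | 2x5 mL | none | none | 6.2.2, 6.2.7.3 |
| Sustained remission | 2x5 mL (follow-up visit) | none listed | only if first was positive | 6.2.4, 6.2.7.3, 6.4 |

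**Visit count.** Section 6.2.2 lists 7 visits. Research serum is taken at 7 − 1 = 6 of them, plus screening. The one visit left out is the one with histology in both gut groups and baseline stool.

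**Could other week-0 blood stand in?** Section 6.2.2 schedules routine inflammatory markers at week 0, but as routine tests and not as stored research serum. The heparin blood is drawn at Ghent only, and "The additional heparin blood samples are used immediately for functional analysis". Neither is described as a substitute for biobanked serum.

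**Interval.** No upper limit between screening and baseline was found in the readable text. The flowchart in section 6.3 and two figures in section 6.2.7.2 could not be read.

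**Drug conditions.** Section 6.1.3 excludes "Exposure to systemic corticosteroid treatment in the last 14 days before the ileocolonoscopy". DMARD exposure is counted over the 3 months before the same procedure. Infections treated with intravenous or oral anti-infectives are counted over 30 or 14 days before the baseline visit. None of these windows is tied to the screening draw.

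Let S be the day of the screening serum, L the last day of systemic corticosteroid and C the day of the ileocolonoscopy.
- Eligibility requires C − L ≥ 14 days.
- On corticosteroid at screening means L ≥ S.
- Hence C − S ≥ C − L ≥ 14 days.

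Such a patient would have washed-out histology, but serum drawn on the drug at least 14 days earlier. The documents do not say how many such patients there are, and there may be none. Section 6.2.1 has eligibility checked at screening, so a site might also decline such a patient rather than wait.

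**Cost of a week-0 sample.** 2 x 5 mL = 10 mL per patient, and 10 mL x 147 = 1,470 mL, about 1.5 L in all. If two of the four screening tubes are moved, screening takes 2 x 5 = 10 mL and week 0 takes 10 mL. The total stays at 4 x 5 = 20 mL.

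**The case against.** The strongest reply is that this is a deliberate choice and a harmless one. Sections 6.2.2, 6.2.7.2 and 6.4 agree, and section 6.6 is a general sentence that does not repeat the exception. A serum sample from before study treatment does exist, with twice the volume of a follow-up sample. CRP and ESR at screening and inflammatory markers at week 0 would show some systemic change between the visits, and medication history is recorded at screening and again if the gap exceeds 4 weeks. Much of this stands, and it limits the point.

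Four stronger readings are tempting, and the documents do not support them:
- **That section 6.6 flatly contradicts the schedule.** It speaks of blood, not serum, and some blood is drawn at week 0, so it is partly met. What remains is that it links this blood to serum calprotectin, for which no week-0 research serum is planned.
- **That accuracy estimates or changes from baseline will be biased.** The plan specifies no sensitivity, specificity or change-from-baseline analysis of serum markers. The problem is a weaker data set for such work, not an error in a stated analysis.
- **That all 147 patients are materially affected.** All lack a week-0 research serum, but the actual gap is unknown and may be short. Section 6.2.7.2 treats more than 4 weeks as a contingency.
- **That the trial's endpoints are touched.** Clinical remission and mucosal healing do not use these samples, nor does the sample size.

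It is also fair that a week-0 tube alone does not guarantee same-day pairing. Section 6.1.3 treats the ileocolonoscopy and the baseline visit as separate reference points, and no readable text requires them, or the stool sample, to fall on the same day. The fix therefore includes recording the dates.

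The reply does not answer why the one visit with histology in both groups goes without serum. The documents give no reason, and routine markers do not replace stored serum for calprotectin.

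**Conclusion.** The point holds as a moderate, inexpensive improvement to the exploratory research in section 6.6. The screening sample is the only research serum from before study treatment. It may precede baseline histology and stool by an interval that the readable text does not limit and that the plan expects may pass 4 weeks, and drug conditions may differ between the two. The gap is at least 14 days for any patient on systemic corticosteroids at screening. The size of the effect cannot be calculated, because the documents give neither the actual intervals nor the number of patients exposed to these drugs at screening. If the visits fall close together, little is lost. The conclusion assumes that no visit window is set in the flowchart or figures that could not be read. A window there would narrow the concern but would not create same-visit pairing.

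**What to change.** - In section 6.2.2, remove the week-0 exception and add 2x5 mL of research serum to the blood draw already scheduled at that visit, taken before the first dose of the study NSAID. Alternatively, move two of the four screening serum tubes to week 0.
- Enter the sample in section 6.2.7.2 and in the baseline row of table 6.4.
- State that the week-0 serum is the baseline value for serum calprotectin and other serum gut markers. The screening EDTA samples for genetics stay where they are.
- Align section 6.6, saying which blood is taken at which visit.
- Record the dates of serum, stool and ileocolonoscopy, so that the intervals can be reported.

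The cost is a short amendment and 10 mL more blood per patient (about 1.5 L over 147 patients), or no extra blood if tubes are moved. If no week-0 serum is added, the lesser remedy is to correct section 6.6, name the screening serum as the pre-treatment value and set a maximum interval from screening serum to ileocolonoscopy. That would settle the wording and limit the gap, but would not give same-visit pairing.

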### 6.2.3 Start of anti-TNF $\alpha$

If a subject starts on anti-TNF $\alpha$  treatment, the timing of the study visits will be recalculated: part B +12 weeks, +24, +36, etc.

### 6.2.4 Remission

If subjects are in remission (ASDAS < 1.3) during the follow-up period on 2 consecutive study visits (with an interval of 12 weeks), subjects are considered to be in sustained clinical remission and golimumab or NSAID therapy will be stopped and a second ileocolonoscopy will be performed in those patients from whom the first colonoscopy showed (subclinical) gut inflammation. During the ileocolonoscopy, for all sites routine biopsies for pathological examination (4 biopsies in ileum, 8 biopsies in colon) and extra biopsies for RNA sequencing (2 biopsies in ileum, 2 biopsies in colon) will be taken. Additional for functional analyses, site specific (only in Ghent University Hospital), also 6 biopsies in ileum and 6 biopsies in colon will be taken. Additional blood samples (3x10mL heparin) will be taken prior to the ileocolonoscopy for simultaneous functional analysis (site specific: only sampling of heparin blood in Ghent University Hospital). A new MRI of the sacroiliac joints will be performed in all patients in which treatment was withdrawn because of sustained clinical remission on 2 consecutive clinical visits. For all those patients the study ends and follow-up and treatment will be foreseen every 6 months in our local Be-Giant register according to the routine clinical practice.

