## 6.2 Study design and procedures

Cfr. infra: 6.3 Flowchart.

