### 6.2.5 Relapse

- Relapse is defined as:

- $\Delta$  ASDAS  $\geq 0,6$  (compared to ASDAS at time of sustained clinical remission) and ASDAS  $\geq 1,3$  (17)

AND

- PASS (= patient acceptable symptom state) for the upcoming 6 months is NO (meaning: would the patient be satisfied if current clinical situation would continue for the next 6 months)

AND

- Expert opinion: the assessing physician believes that  $\Delta$  ASDAS reported by the patient is most probably related to a relapse of spondyloarthritis. If not, an alternative hypothesis/probable diagnosis must be provided.

- In case of relapse, the time point will be registered in the study, extra blood samples will be drawn (2x5mL serum; site specific: 3x10mL heparin blood only in Ghent University Hospital) and the

subjects will be treated according to the routine clinical practice. In reality, this will most likely match the last remission-inducing treatment of the subject.

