### **6.2.6 No remission achieved**

When the subject is still not in sustained remission after 48 weeks of golimumab treatment, defined as ASDAS < 1.3 on 2 consecutive study visits, the patient will stop participating in this study and will be followed in the routine clinical practice.

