### **6.2.7 Procedures**

#### **6.2.7.1 Screening visit**

- ICF
- Check fulfillment of the inclusion and exclusion criteria
- Anamnesis
- Medical and family history
- Demographic data
- Symptom duration
- Current and past medication (NSAID): dosage and duration
- Clinical examination:
  - o weight, length, vital symptoms (blood pressure, heart frequency)
  - o BASMI
  - o Total tender and swollen joint count (TJC/SJC) (78)
  - o Dactylitis assessment
  - o MASES + plantar fascia + quadriceps and patellar tendon
- Assessment of work participation (site-specific: only in Ghent University Hospital).
- Questionnaires: Bath Ankylosing Spondylitis Disease Activity Index (BASDAI), Bath Ankylosing Spondylitis Functional Index (BASFI), Patient global assessment of disease activity, patient global pain assessment. Site-specific (only in Ghent University Hospital): Work Productivity and Activity Impairment (WPAI), health care consumption, EQ5D.
- Laboratory investigation (incl. 4x5mL serum + 3x4mL EDTA for additional research)
- Imaging: MRI SI joints (if not already done), chest X-ray
- Mantoux tuberculin test
- Pregnancy test for female subjects (on blood sample)

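### Section 6.2.4 closes the study at treatment withdrawal in sustained remission, yet 6.2.5 counts relapse from that point as study data; the supplied text gives neither follow-up length nor register link

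*Combined protocol and SAP*

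**What the plan says.** All references are to the combined protocol and SAP.

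- **6.2.4 Remission.** Sustained remission is ASDAS below 1.3 at two consecutive visits 12 weeks apart. Golimumab or the NSAID is then stopped. An MRI follows, with a second ileocolonoscopy if the first was positive. The section closes: "For all those patients the study ends and follow-up and treatment will be foreseen every 6 months in our local Be-Giant register", under routine practice.
- **6.2.2 Baseline and follow-up.** "Maximal study duration for a subject is 12 months".
- **6.2.5 Relapse.** The ASDAS part of the definition is a change "compared to ASDAS at time of sustained clinical remission"; PASS and expert opinion must also be met. The section continues: "In case of relapse, the time point will be registered in the study, extra blood samples will be drawn".
- **6.2.2, 6.2.7.3, 6.4 and 6.6.** Each plans samples or assessments at relapse.
- **3.3 and 3.2.** The hypothesis has two parts, and one is a shorter time to relapse after anti-TNF is stopped in patients with gut inflammation. Secondary objective 3 relates gut inflammation to remission induction and to relapse.
- **10.3 Statistical analysis.** This names who will do the analysis. It gives no method or censoring rule for relapse.

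**The concern.** Relapse is defined relative to the moment of sustained remission, so it can only happen afterwards. That moment is also when 6.2.4 takes the patient out of the study. One section therefore ends observation at the time origin of an outcome that another section says the study will record.

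At stake is the time-to-relapse part of the hypothesis and the relapse part of secondary objective 3. If sites follow 6.2.4 as written, whether a relapse enters the trial data, which of the 6.2.5 items are collected, and when a relapse-free patient is censored are all left to local practice. Differences in how long or how closely patients are watched could then be confused with differences in time to relapse.

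**Working it through.** **1. The 12-month cap.** Golimumab starts at week 4 if the NSAID target is not met (6.2.2). Section 6.2.6 sets the limit of the golimumab phase: "When the subject is still not in sustained remission after 48 weeks of golimumab treatment". The longest path is 4 + 48 = 52 weeks. Twelve months is 365.25 / 7 = 52.2 weeks. The cap therefore equals the longest treatment path and holds no allowance for follow-up after it.

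**2. When sustained remission can be declared on golimumab.** Section 6.2.3 says that "the timing of the study visits will be recalculated: part B +12 weeks, +24, +36, etc". With a start at week 4, visits fall at study weeks 16, 28, 40 and 52. A patient who has just failed the NSAID target is not in remission at week 4, so the earliest qualifying pair is +12 and +24 weeks. Sustained remission can be declared at:

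- 4 + 24 = week 28
- 4 + 36 = week 40
- 4 + 48 = week 52

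**3. First register visit after withdrawal.** Taking 6 months as 26 weeks:

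| Golimumab stopped (week) | First register visit (week) |
|---|---|
| 28 | 28 + 26 = 54 |
| 40 | 40 + 26 = 66 |
| 52 | 52 + 26 = 78 |

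None falls within 52 weeks at nominal timing. Visits carry a window of ±2 weeks, so the earliest could just reach week 52. A golimumab start later than week 4 would move every date later.

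**4. NSAID remitters.** Visits 12 weeks apart allow sustained remission at week 16, 28, 40 or 52, with first register visits at about week 42, 54, 66 or 78. These patients bear on secondary objective 3 at most, because the hypothesis concerns stopping anti-TNF.

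**5. The sections side by side.**

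| Question | 6.2.4 with 6.2.2 | 6.2.5 |
|---|---|---|
| Status after withdrawal | Study ended; register, routine practice | Relapse time recorded by the study, blood drawn |
| Start of relapse clock | Same moment as study end | ASDAS at sustained remission |
| Frequency of assessment | Every 6 months | Not given |
| Length of relapse follow-up | Not given | Not given |
| Register data become trial data | Not said | Not said |

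Read literally, in-study time at risk is essentially zero. It is not exactly zero, because the MRI and any second ileocolonoscopy come after the decision to stop and are not timed. If relapse is found only at register visits, its date is known to within about 26 weeks.

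**The case against.** The best defence is that the word study is used loosely. Section 6.2.4 sends every withdrawn patient to a named register at a stated interval, and several sections plan sampling at relapse. The cap matches the treatment phase exactly. Read together, the treat-to-target phase ends, follow-up continues in the register, and a relapse triggers recording and sampling. That is probably what was meant, and event-triggered samples are not in themselves a contradiction. But this reading needs a rule that the supplied text does not contain: that register findings are trial data, and for how long they are sought.

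A reader might infer that all relapse data will be lost. The documents do not support that. It follows only from the literal wording, and the move to a named register makes it the less plausible reading. A reader might also infer a measurable loss of precision in the relapse comparison. The documents give no relapse times, remission rates or follow-up length, so no such figure can be drawn from them. Nor can the weeks left before the cap be counted as in-study follow-up, since 6.2.4 has already ended the study.

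Missing text also limits the point. Section 6.2 refers the reader on: "Cfr. infra: 6.3 Flowchart". That figure is not shown, and consent pages were removed. A follow-up length or register link could appear there. It would not undo the conflict between 6.2.4 and 6.2.5.

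PASS is not named in the questionnaire list of 6.2.7.1. This is minor, since 6.2.5 defines it and the relapse row of 6.4 marks questionnaires.

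**Conclusion.** The point holds as a conflict between stated rules. Section 6.2.4 ends the study at the moment from which 6.2.5 measures relapse, and 6.2.5 still treats the relapse time as study data. The 6-monthly frequency is not itself the defect. What the supplied text leaves open is how long relapse is followed and whether the register feeds the trial dataset.

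The size that can be stated is calendar time: essentially no in-study time at risk on the literal reading, and a first register visit at about week 54, 66 or 78 for golimumab remitters. These weeks assume a golimumab start at week 4, nominal visit dates and 26-week register spacing. The textual conflict depends on none of these assumptions.

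Importance is secondary. Relapse is not among the endpoints in 3.4 and 3.5, is not a primary objective in 3.1, and is not the basis of the sample size in 10.1.

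**What to change.** Reconcile 6.2.2, 6.2.4 and 6.2.5 by one of two routes.

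1. **Keep time to relapse.** State that relapse is ascertained as trial data for a defined period after withdrawal, through the existing register visits and any unscheduled relapse visit. Record there the 6.2.5 items (ASDAS, PASS, expert opinion), the date of the last relapse-free assessment and the date of the first assessment showing relapse. Analyse time from treatment stop by a method that allows for 6-monthly spacing, for example an interval-censored model.
2. **Drop it.** Remove time to relapse from the hypothesis and state that relapse in secondary objective 3 rests on register data.

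Either route needs a protocol amendment. The first adds a few data fields and some analysis work, but no scheduled visits beyond those the register already has. Its larger cost is giving off-treatment register visits trial status: the sponsor would have to confirm that consent, safety reporting and the register cover the whole period at all three sites. The supplied text does not show this.
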